Blood draws and urine tests for routine screening, including pregnancy testing. Participants will undergo a blood draw for a comprehensive metabolic panel, pregnancy test, liver panel. These tests prior to the psilocybin session allow the investigators to ensure that there are no contraindications to subjects' participation in the study, such as liver function abnormalities which could produce higher than expected levels of psilocybin. Higher levels of psilocybin may produce prolonged duration or greater intensity of subjective effects. Weighing the risks and benefits of a blood draw versus potentially unpredictable levels of psilocybin, the liver panel conveys more benefits than risks. Serum pregnancy and / or urinary pregnancy testing will be conducted at the screening visit to avoid the risk of unintended psilocybin exposure in utero. Less than 50mL will be drawn per collection. There will be a single blood draw over the course of study. The blood draw may produce temporary discomfort as a result of sampling blood, and discomfort or bruising at the blood drawing site. The urinary drug screen is necessary to verify abstinence from illicit substances or nonprescription stimulants prior to the psilocybin session.

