Routine labs: Screening is necessary to assess participant eligibility and to uncover sometimes unknown contraindications. We minimize risk by having only skilled medical staff conduct the brief physical examination rule out any cardiac abnormalities.

Urine toxicology and blood draws. We minimize medical risk by having skilled nurses and phlebotomists do our blood drawing. If a blood draw produces temporary discomfort, then nursing staff can offer ice or cool compresses. There is also a remote possibility of inflammation or infection at the blood drawing site. Liver panel results will allow the investigators to detect poor metabolism, which could produce higher than expected levels of psilocybin. Higher levels of psilocybin may produce prolonged duration or greater intensity of subjective effects. Weighing the risks and benefits of a blood draw versus potentially unpredictable levels of psilocybin, the liver panel conveys more benefits than risks. The urinary drug screen is necessary for verifying the participant's report of current substance use and to eliminate potential risks of interactions of the study medications with other medications needed by the participant. Subjects are informed of this testing in advance of

Page 15 Version 1.16, July 18, 2022

the screening appointment and may choose to not participate in the study.

Study questionnaires. The research staff will inform all participants that they may take breaks while completing questionnaires, or stop if they are experiencing too much frustration, or anxiety. Participants may take breaks from completing measures and online tasks. Ratings will be administered with sensitivity by trained staff, either on paper instruments or online portals utilizing secure servers and data capture systems. All online responses will be captured on secure servers. This use of online measures speeds up the assessment process and seems to reduce some subject stress. All information will be kept strictly confidential.

Returning to work. Participants will be required to wait 48 hours after a medication dosing session before returning to work.

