Medication contraindications will include anti-seizure medications, insulin and oral hypoglycemics, hypertension medications that act on the central nervous system (clonidine and aldomet specifically), cardiovascular medications and the following psychotropic medications: anti-psychotics (first and second generation agents), anti-depressants and mood stabilizers. Psychotropic medications cannot be taken in the previous two weeks, with Prozac (fluoxetine) not being taken within the last 5 weeks prior to receiving any study agents. Participants may only take prn (as needed) benzodiazepines (i.e., lorazepam) up to three days before the session. Participants will refrain from taking any medications the day of either the experimental psilocybin medication dosing or active-placebo-control medication dosing session, except prescribed opiate pain medication or over-the-counter non-narcotic pain medication at any time. It will also be necessary to refrain from drinking alcoholic beverages the day before, the day of, and the day after each medication dosing session.

Physical exam, and blood and urine tests are required at the screening visit to meet eligibility criteria. As part of the study participants will have a physical examination, and screening blood (including a comprehensive metabolic panel, chemistries, hematological tests) and screening urine toxicology tests (for medications as described in Section 1.3.3.8; and pregnancy for female participants of childbearing potential). These results will also become part of the research case record.

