6.2. Study schedule for participants by visit

6.2.1. Screening and Informed consent

Prior to participation in this research, subjects will receive a brief secure online screening survey and then if eligible, will be screened by phone to determine preliminary eligibility. All subjects will be informed about the phone screening and what the screening process involves.

All potential participants will be told that we collect demographic information, relevant medical history, and psychiatric history during the screening process. Screening data are entered directly into a secure online database and are considered a source document.

All seemingly eligible subjects will be told that they need to come in for baseline screening visit, and will be informed about baseline questionnaires, clinician assessment, blood draw, and pregnancy test (if applicable) to ensure their eligibility. Subjects are free to decline participation at this point or to discontinue participation at any future point and to withdraw from consideration.

Some potential participants live in another state, and it may not be feasible to have them come for an in-person screening visit. In this case we will conduct the screening interview uligescure video communication platforms. We will ask these participants to send us their most recent physical, and blood work (recent as of 1 month from the screening visit will be allowed). This will be faxed to the PI and reviewed for potential participation. A remote urine test will be ordered for the screening process of remote participants.

Prior to obtaining informed consent, the PI will confirm that the participant meets all study inclusion and exclusion criteria. The investigator or research staff member obtaining consent will ask the participant to provide a brief summary of the study to ensure they understand what is being asked of them and any potential risks and benefits.

Note that if a female subject is pregnant, or breast-feeding, or does not agree to use an approved birth control method (i.e., oral, injectable, or implant birth control, condom, diaphragm with spermicide, intrauterine device, tubal ligation, abstinence, or partner with vasectomy) she will be excluded.

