6.2.3. Medication Dosing session (Visit 3)

Procedures for psilocybin administration and the conduct of the session will be similar to procedures used in studies with psilocybin conducted at New York University, Johns Hopkins, and Yale. Participants will be instructed to consume a low-fat breakfast before reporting to the clinic room for the psilocybin sessions. Before psilocybin administration, urine pregnancy test will be conducted in females of childbearing potential, and a negative pregnancy test will be required in order to continue in the medication session. Participants and staff will also complete pre-session questionnaires. Before each psilocybin session, study personnel will interview the participant. If the investigator believes that the session is contraindicated, the session will be cancelled or postponed.

Psilocybin will be administered in opaque gelatin capsules with approximately 100 ml water. At least one therapist, under the supervision of the investigators, will be present in the room and available to respond to participants' physical and emotional needs during the full course of the session (at least 7 hours). A physician on the study team will be immediately available via pager or mobile phone for at least 3 hours or until the peak effects of psilocybin have subsided, whichever is longer.

During the session, participants will lie on a couch, wear eyeshades, and listen to a program of music through headphones. The participant will be encouraged to focus her or his attention inward. The eyeshades and music are intended to encourage this inward reflection. Heart rate and blood pressure will be measured pre drug administration, at 30, 60, 90, 120 minutes after drug administration, and then at least hourly until at least 6 hours after drug administration and until drug effects have subsided. Heart rate and blood pressure assessments will be obtained after the participant has been sitting or recumbent for at least 5 minutes. Sessions are expected to last approximately 7 to 10 hours. A sample schedule for the medication dosing session is as follows:

Approximate Time	Procedure or Action
09:00	Urine pregnancy test for females of childbearing potential,
	participant acclimates to environment, completes measures.
09:30	Baseline BP, Pulse, Temp.
	Medication Administration.
	Begin video recording.
10:00	BP, Pulse
10:30	BP, Pulse
11:00	BP, Pulse
11:30	BP, Pulse
12:30	BP, Pulse
13:30	BP, Pulse
14:30	BP, Pulse
15:30	BP, Pulse
16:30	BP Pulse.

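### The randomized phase schedules its only urine drug screen at screening, nominally 14 to 21 days before dosing, so the screen cannot verify abstinence up to the session

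*Combined protocol and SAP*

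**What the plan says.** **Purpose of the test.** Section 1.3.3.5 (blood draws and urine tests) states: "The urinary drug screen is necessary to verify abstinence from illicit substances or nonprescription stimulants prior to the psilocybin session". Section 1.3.3.8, under urine toxicology, adds that the screen is "necessary for verifying the participant's report of current substance use and to eliminate potential risks of interactions" of study drug with other medicines. Elsewhere in 1.3.3.8 the drug screen is described as part of establishing eligibility.

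**Rule it supports.** Section 3.1.4 requires participants to stay off recreational drugs for the duration of the study.

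**Timing of the test.**
- Section 3.1.4: "Physical exam, and blood and urine tests are required at the screening visit to meet eligibility criteria". The same paragraph names urine toxicology among those screening tests.
- Section 6.2.1, for people living out of state: "A remote urine test will be ordered for the screening process of remote participants".
- Section 3.1, randomized-phase schedule: the urine screen row has a single mark, under Screen (approximate study day -21 to -14). Pregnancy testing has its own row, marked at Screen and at Medication.

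**Dosing day.** Section 6.2.3 lists the checks before the capsule. On urine it says: "Before psilocybin administration, urine pregnancy test will be conducted in females of childbearing potential, and a negative pregnancy test will be required". It also provides for an interview by study personnel, and "Heart rate and blood pressure will be measured pre drug administration". The sample timetable in that section shows no toxicology test.

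**The concern.** A urine sample can only speak to the time before it was collected. The protocol says abstinence before the session needs verifying, and that the participant's own report needs checking, but it takes the sample two to three weeks early. Nothing listed afterwards tests for a substance.

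The protocol treats other screening results as going out of date. Pregnancy is tested again on the dosing day, a COVID antigen test is done that morning (section 2.2), and the suicidality scale is repeated at every visit. Toxicology is not repeated. For a remote participant, no drug screen at the study site is scheduled before the randomized dose.

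At stake is the safety of someone who uses a barred substance between screening and dosing and does not report it. Section 1.3.3.8 itself links the screen to interaction risk.

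**Working it through.** The protocol gives no figure for this interval, so there is none to reproduce. The check is a reading of the schedule followed by subtraction of days.

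**Inputs**
- Dose: Day 0, visit V3 (section 3.1 schedule).
- Screening: printed as -21-14, read as Day -21 to Day -14 (same table).
- V2: Day -1 (same table).
- Numbers: 30 target completers, 36 enrolled (section 9.2).
- Visit times are described as estimates (section 6.2.6).

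**Step 1: is any drug screen placed between screening and the dose?** The relevant texts side by side:

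| Section | Urine test | When |
|---|---|---|
| 1.3.3.8 | toxicology | participants told of it ahead of the screening appointment |
| 3.1.4 | toxicology and pregnancy | screening visit |
| 6.2.1 | remote urine test | screening |
| 3.1 schedule | urine screen | Screen column only |
| 3.1 schedule | pregnancy | Screen and Medication |
| 6.2.3 | pregnancy | before the capsule |

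No text schedules toxicology at V1, V2 or V3. The table was extracted from PDF and is visibly incomplete: preparation psychotherapy is marked only at V1, although section 6.2.2 specifies two preparation visits. A blank cell is therefore weak evidence alone. Sections 3.1.4, 6.2.1 and 6.2.3 support the same reading without the table.

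**Step 2: nominal gap, last drug screen to dose**

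Gap = day of dose − day of sample.
- Latest screening: 0 − (−14) = 14 days.
- Earliest screening: 0 − (−21) = 21 days.

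**Step 3: gap with one repeat**
- At V2: 0 − (−1) = 1 day.
- On arrival at V3: 0 − 0 = 0 days.

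**Step 4: number of extra tests**

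One per participant gives 30 (completers) to 36 (full enrollment), plus one for each session that is postponed and rescheduled.

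**Step 5: the open-label phase.** The section 6.3 schedule marks a urine screen in the Medication column. That table has no separate pregnancy row, so the entry could be either test. It is not used as evidence here.

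**The case against.** The strongest reply is that purpose and timing already agree. The sentence in section 1.3.3.5 closes a paragraph on routine screening, section 1.3.3.8 ties the test to eligibility, and a test at screening is literally before the session. On this view a second test is a preference. The reply is right that the protocol does not contradict itself, and a reader who infers a contradiction goes too far. But the stated job is verifying abstinence ahead of the session, and a sample cannot vouch for the weeks after it.

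Other controls exist:
- contact by staff at least weekly (1.3.3.8);
- an adult who watches for behavior change (4.1 g);
- medication checks at some visits (3.1.4);
- exclusion of current substance abuse disorder, of psychedelic use in the prior 12 months and of tramadol (4.2);
- the pre-session interview and vital signs (6.2.3).

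These lower the likely yield, and not all depend on self-report. None tests for a substance.

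A reader might also infer that the medication limits go unverified, because section 3.1.4 says "Psychotropic medications cannot be taken in the previous two weeks" and "Participants may only take prn (as needed) benzodiazepines (i.e., lorazepam) up to three days before the session". The documents do not support building the point on that. They give no test panel and no detection window. We therefore cannot say that a urine screen would detect antidepressants, antipsychotics or mood stabilizers, or that a positive on Day -1 or Day 0 could separate benzodiazepine use before the three-day limit from use after it. Antidepressant washout is an entry requirement (five half-lives plus 2 weeks; 3.1.4 and 4.1 h), backed by a written provider plan and weekly calls during taper (1.3.3.3).

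Finally, the therapist manual (1.3.3.8) and the Medication Day Case Report Form (6.2.3) are not among the documents. A test recorded only there cannot be excluded.

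**Conclusion.** The point holds as a minor participant-safety gap. As scheduled, the drug screen supports eligibility but cannot verify abstinence from illicit drugs or unprescribed stimulants up to the randomized session. The nominal untested interval is 14 to 21 days, and actual intervals may be shorter or longer.

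This rests on two assumptions: that the urine screen row means toxicology, which its separation from the pregnancy row and the text of section 3.1.4 support; and that no unlisted test exists in the documents we have not seen.

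The documents give no rate of substance use, so no number of affected participants can be stated, and the expected yield is low. A reader might infer that the trial's result is compromised. Nothing here supports that: the sample size and the primary MADRS comparison are unaffected.

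**What to change.** Keep the screening test for eligibility. Add one repeat point-of-care urine drug screen at V2 (Day -1) if that visit is in person, otherwise on arrival at V3. Read it before the capsule is given. List it in the section 3.1 schedule and among the pre-dose checks in section 6.2.3, and name the panel.

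If the result is positive for a non-permitted substance, postpone under the existing section 6.2.3 rule for contraindicated sessions. Check positives that prescribed opiates or permitted benzodiazepines could explain against the medication record; those do not count as failures.

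Leave the randomization procedure as it is. The pharmacy randomizes after the preparation sessions and packs the capsules (section 6.1), and the sample timetable allows only 09:00 to 09:30 between arrival and dosing, so holding randomization for a dosing-morning result would disturb that workflow. A participant already randomized keeps the assignment and stays in the intent-to-treat set.

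The sponsor should also state whether the open-label dosing-day urine screen in section 6.3 is toxicology or pregnancy. If a pre-dose drug screen is already done under the manual or case report form, listing it in sections 3.1 and 6.2.3 is the whole fix.

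**Cost.** About 30 to 36 extra urine tests at existing visits, and a short wait when the test falls on the dosing morning. An occasional postponement would lengthen time off antidepressants for participants who had stopped them. The test also creates one more sensitive record on a licensed clinician (section 1.3.3.7), to be held under the study code and the existing confidentiality protections.

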1.3.3.6. Reproductive Risks

While some women who choose to participate in the study will be post-menopausal, so the pregnancy will not be possible, pre-menopausal women who could bear children could be at reproductive risk. There have been no systematic studies of the effect of psilocybin in utero, but also no case reports of birth defects resulting from psilocybin use. Thus, the reproductive risks seem minimal, but are not well characterized. We will screen all participants who are pre-menopausal women with pregnancy tests, and counsel them to use birth control until after their medication session.

1.3.3.7. Risks of privacy and confidentiality

There is a special potential risk to study participants because of their profession. Doctors in some states are required to report any mental health condition that may affect their performance to the state licensing board. If not mitigated, these risks could lead to reputational damage and even damage to their employability. The same requirement is not mandated for advance practice providers or nurses, but those clinicians could still face reputational damage if their participation in this study were made public. To mitigate this risk, we have applied for an FDA Certificate of Confidentiality, and all data will be entered using a study code.

1.3.3.8. Minimizing participant risks

The anticipated risks and risk mitigation strategies that will be used are summarized in the Table below.

Anticipated risk	Risk mitigation strategies	Occurrence of risk in recent published studies since 2000
Changes to any treatments a participant is receiving prior to study screening and enrollment	 Clear communication with potential participants about existing treatments (for example need to taper SSRI before study entry). Coordination between PI and participants mental health provider. 	Published studies do not report numbers of participants who had complications related to changing treatments prior to screening.
Worsening of participant mental health symptoms during the study	 Weekly phone calls from study staff to check in re participant well-being are part of the study procedures. Mental health symptoms will be assessed by study therapists during all preparation and integration psychotherapy sessions, and therapists will discuss with participants and the study team (at a weekly meeting or urgently with the PI) any issues that may warrant a change in study procedures. 	This risk has not been reported in published studies since 2000.
Increase in participant suicidality during the study	 All participants will be screened with the Columbia Suicidality Screening instrument at preparation, medication days, integration sessions, and at follow up measurements. If an increase in suicidality is measured, study staff will notify the PI immediately and arrangements for appropriate evaluation will be made with the attending psychiatrist on call at Harborview Medical Center. 	This risk has not been reported in published studies.
Intense psychological reactions during the medication session	 All study therapists will have training specifically for this issue. the therapist manual lays out first-line and second-line interventions (which are non-pharmacologic), as well as indications about when to notify the PI [name]. These interventions are based on consultation and experience at other academic centers where research with synthesized psilocybin has been conducted (NYU, Yale, Johns Hopkins). 	This risk has been reported in up to 40% of participants. In all instances, these reactions have been managed with non-pharmacologic interventions, and

Page 12 Version 1.16, July 18, 2022

		the reactions have been transient.
Discomfort resulting from study questionnaires	1. All participants will be informed that they may take a break at any time from questionnaires and that study staff are available to discuss issues that warrant follow up.	This risk has not been reported.
Confidentiality of participant identity	1. Because doctors in some states are required to report any mental health condition that may affect their performance to the state licensing board, we have submitted a request to the FDA for a Certificate of Confidentiality.	No prior studies have had participant inclusion criteria that specify doctors and nurses.
Reproductive risks	1. All female potential participants will be asked about their menopausal status at screening, and pre-menopausal participants will undergo a pregnancy test.	As noted above, the reproductive risks seem minimal, although they are not well characterized.
Length of study for subjects who were taking medications prior to study entry and who are randomized to placebo	1. The study team will clearly communicate with potential subjects during consent conversations to ensure eligible subjects know they may be off their medications longer if they are assigned the placebo group and then chose the open-label psilocybin session following un-blinding. We will recommend that individuals taking medications that need to be stopped, discuss this with their provider(s), family, and any other trusted people, prior to agreeing to participate in the study.	This risk has not been reported.
	2. Minimize the time for subjects who are randomized to the placebo group to an open-label psilocybin session. We anticipate that arranging and scheduling an open-label psilocybin session will take 1-2 weeks. During this time, subjects will be followed weekly and will have an additional preparation psychotherapy session, and every weekly contact will include administration of the C-SSRS suicidality screen to minimize risk to these subjects. We judge that this additional risk of 1-2 weeks off antidepressants is acceptable given	

Page 13 Version 1.16, July 18, 2022

that these subjects will be monitored closely.	

A detailed therapist manual outlines procedures for every contact session with participants, and for participant issues that could represent risk, the manual outlines responses to minor, moderate, and severe side effects with first-line, second-line, and indications to call the PI by phone for urgent or emergent issues. Research staff including the investigators and PI will be available to evaluate any change in a participant's condition. Participants will be asked to contact us at any time if any unpleasant effects occur and will be contacted by study staff at least weekly during study participation. A study physician will be at the study site on medication dosing days to manage psychiatric emergencies.

Synthesized psilocybin: Reviews of the drug and the literature indicate that the physiological and psychological effects are transient. The patient will be monitored at all times by trained research and/or medical staff. The study medical doctors and nursing staff who are trained in dealing with drug challenge studies (such as ketamine, psilocybin, yohimbine, and various cannabis compounds) will remain in attendance during the entire session. Participants will be asked to remain on the CNRU until effects wear off. Procedures will be immediately stopped if participants request or if they are exhibiting significant distress. To minimize risk associated with synthesized psilocybin, participants will undergo a thorough screening for contraindicated psychological conditions or interacting medications. Dosing with psilocybin must be performed in a setting that minimizes distraction and interruption, and the participant must be attended following the dose by research staff trained in providing reassurance and a safe environment until the effects of the single dose have dissipated.

The PI may prescribe a designated rescue medication in the event of symptoms that require it during or after the medication dosing session. Rescue medications may be a benzodiazepine, zolpidem, or other anxiolytic or sedative according to the physician's clinical judgment.

Following the investigator brochure, although there have been no reports of their use in well-reported clinical trials with oral psilocybin, medications will be available for the treatment of causal symptomatic hypertension, agitation, or severe psychosis. Typically, these supplies are two dosage unitsof labetalol, nitroglycerin, lorazepam and/or diazepam, and risperidone or similar orally- disintegrating antipsychotic.

If any participant presents with an adverse reaction to the psychopharmacological agent as reported by them or assessed by a member of the research team, we will discontinue the study and call for medical assistance. Finally, the participant may be withdrawn from the study if his/her withdrawal is in the best interests of either the participant or of the research (e.g., due to a medical condition making the procedures unsafe or any condition making interpretation of the results difficult).

Niacin: (active-placebo-control agent): There is no reason to believe that niacin would exacerbate symptoms of depression or burnout or PTSD. Participants will be informed about Niacin's potential side effects, and they will be monitored throughout the drug administration visits. The rationale for using an active-placebo-control agent rather than active low dose of psilocybin (ranging 2mg -4mg), which have been used in the recent palliative care studies is because a partial response has been reported even with these low doses.

Page 14 Version 1.16, July 18, 2022

Changes or delays in treatments being received prior to screening: Participants will be asked to refrain from starting new medications to allow the participant and this study to safely proceed. If medically warranted, or the participant begins to experience a decline, or their provider believes a treatment change is necessary, then the participant will be withdrawn from the study and encouraged to seek treatment.

Involuntary holding, overnight for safety: The medical staff will closely monitor the participant's medical status during study administration. The staff take whatever medical steps are safely possible to reduce the need for an additional holding period including ongoing evaluations during the testing period. However, if there was concern about participants being a risk to themselves or others during the study, or if investigator feels it is medically necessary, and/or if the participant is not compliant, then the participant may need to be involuntarily held for his/her own safety. If a participant requires overnight observation, the participant's medication would be unblinded to maximize the information available to the treating inpatient team. Participants will be discharged after the study physician believes that it is safe to do so.

Emotional Responses and Discomforts During Psilocybin Medication Session, and follow-up appointments: Trained staff will be on hand to help participants deal with their responses to the study. The therapist manual outlines first- and second-line interventions for emotional responses or any psychological reactions that may be experienced. In studies since 2000 conducted at academic research centers, no participants required 'rescue' medication for psychological reactions—they were all managed with non-pharmacologic interventions.

Administration and follow-up appointments: Only the trained clinical staff will conduct such sessions. Staff will assist patients who require help with their anxiety. The anxiety experienced is no more than normally reported in any standard therapeutic session.

Psychiatric evaluation and clinical assessments: All participants must first give permission for the investigators to review medical records and later undergo a psychiatric evaluation and a urinary drug screen to ensure that participants are eligible to be in the study. We will try to schedule and to complete tasks quickly. Each participant is told that he/she does not have to answer any question that he/she does not want to answer, but that the questions about suicidal ideation and behaviors, including the complete C-SSRS, are required to participate in this study. Only the trained clinical will conduct these evaluations and all exercise utmost sensitivity.

Routine labs: Screening is necessary to assess participant eligibility and to uncover sometimes unknown contraindications. We minimize risk by having only skilled medical staff conduct the brief physical examination rule out any cardiac abnormalities.

Urine toxicology and blood draws. We minimize medical risk by having skilled nurses and phlebotomists do our blood drawing. If a blood draw produces temporary discomfort, then nursing staff can offer ice or cool compresses. There is also a remote possibility of inflammation or infection at the blood drawing site. Liver panel results will allow the investigators to detect poor metabolism, which could produce higher than expected levels of psilocybin. Higher levels of psilocybin may produce prolonged duration or greater intensity of subjective effects. Weighing the risks and benefits of a blood draw versus potentially unpredictable levels of psilocybin, the liver panel conveys more benefits than risks. The urinary drug screen is necessary for verifying the participant's report of current substance use and to eliminate potential risks of interactions of the study medications with other medications needed by the participant. Subjects are informed of this testing in advance of

Page 15 Version 1.16, July 18, 2022

the screening appointment and may choose to not participate in the study.

Study questionnaires. The research staff will inform all participants that they may take breaks while completing questionnaires, or stop if they are experiencing too much frustration, or anxiety. Participants may take breaks from completing measures and online tasks. Ratings will be administered with sensitivity by trained staff, either on paper instruments or online portals utilizing secure servers and data capture systems. All online responses will be captured on secure servers. This use of online measures speeds up the assessment process and seems to reduce some subject stress. All information will be kept strictly confidential.

Returning to work. Participants will be required to wait 48 hours after a medication dosing session before returning to work.

